4.1.5. Handling of Missing and Incomplete Data

For response endpoints, all nonresponders, as well as all participants who are missing postbaseline values, will be defined as nonresponders for the NRI analysis.

For continuous endpoints, any participant who is missing postbaseline values may have missing data handled using MMRM under the missing-at-random assumption. MMRM model implicitly adjusts for missing data through a variance-covariance structure.

For other endpoints, missing observations will be handled as detailed in the specific sections addressing each analysis.

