7.4. Analysis of Secondary Efficacy Parameters

7.4.1. Secondary Efficacy Measures

7.4.1.1. SCORing Atopic Dermatitis

SCORAD is a tool to assess the extent and severity (ie, intensity) of eczema and will be completed before, during, and after treatment has begun to determine whether the treatment has been effective. This will be performed during all VC study visits, starting at baseline.

- To determine extent, the rule of 9 or handprint method is used to calculate the eczema affected area (A) as a percentage of the whole body.
- To determine intensity, the intensity of each of the following signs of redness, swelling, oozing/crusting, scratch marks, skin thickening (lichenification), dryness (this is assessed in an area where there is no inflammation) is assessed as follows:
 - None (0)
 - Mild (1)
 - Moderate (2)
 - Severe (3)

Intensity scores are added together to give “B” (maximum score of 18).

- Subjective symptoms, that is, itch and sleeplessness, are scored by the participant using a VAS where “0” is no itch (or no sleeplessness) and “10” is the worst imaginable itch (or sleeplessness).

These scores are added to give “C” (maximum score of 20).

Total score gives approximate weights of 60% to intensity and 20% each to extent and subjective signs (ie, insomnia, etc) for the participant and will be calculated as follows:

Total score = A / 5 + (7 × B) / 2 + C.

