7.4.1.5. Patient-Oriented Eczema Measure

The POEM is a 7-question quality-of-life assessment that asks how many days the participant has been bothered by various aspects of their skin condition during the past 7 days ([Charman et al 2004](#)).

Each of the 7 questions carries equal weight and is scored from 0 to 4 as follows:

- No days = 0
- 1 to 2 days = 1
- 3 to 4 days = 2
- 5 to 6 days = 3
- Every day = 4

The POEM is calculated by summing the score of each question resulting in a maximum of 28 and a minimum of 0. The meaning of POEM scores can be categorized as follows:

- 0 to 2 = Clear or almost clear
- 3 to 7 = Mild eczema
- 8 to 16 = Moderate eczema
- 17 to 24 = Severe eczema
- 25 to 28 = Very severe eczema

If 1 question is left unanswered, this is scored 0, and the scores are summed and expressed as usual out of a maximum of 28. If 2 or more questions are left unanswered, the questionnaire is not scored. If 2 or more response options are selected, the response option with the highest score should be recorded.

The total POEM score and POEM scores in each category will be summarized by visit and by treatment.

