7.4.1.8. EQ-5D-5L

The EQ-5D-5L ([EuroQol Research Foundation 2017](#)) is a validated, self-administered, generic utility questionnaire wherein participants (adolescents and adults) rate their current health state based on the following criteria (dimensions): mobility, self-care, usual activities, pain/discomfort, and anxiety/depression.

During all VC period study visits (starting at screening) and at specific LTS visits (Weeks 12, 24, 36, 52, and follow-up visit), the participant will be asked to indicate his/her health state over the past 7 days.

Missing values will not be imputed. The categorical outcomes for the 5 dimensions (mobility, self-care, usual activity, pain/discomfort, and anxiety/depression) will be summarized. The change from baseline in EQ-5D VAS score will be analyzed.

7.4.1.9. Work Productivity and Activity Impairment Questionnaire: Specific Health Problem Version 2.0

The WPAI:SHP v2.0 ([Reilly et al 1993](#)) questionnaire is a validated 6-item instrument, completed during all site visits starting at screening, during the VC period, and at specific LTS visits (Weeks 12, 24, 36, 52 and follow-up visit) that measures the effect of overall health and specific symptoms on productivity at work and regular activities outside of it during the past 7 days.

WPAI outcomes are expressed as impairment percentages, with higher numbers indicating greater impairment and less productivity, i.e., worse outcomes, as follows:

Questions:

- 1 = currently employed
- 2 = hours missed due to AD
- 3 = hours missed other reasons
- 4 = hours actually worked
- 5 = degree AD affected productivity while working
- 6 = degree AD affected regular activities

Scores:

Multiply scores by 100 to express in percentages.

- Percent work time missed due to AD: $Q2 / (Q2 + Q4) \times 100$
- Percent impairment while working due to AD: $Q5 / 10 \times 100$
- Percent overall work impairment due to AD: $[Q2 / (Q2 + Q4)] + ((1 - [Q2 / (Q2 + Q4)]) \times (Q5 / 10)) \times 100$
- Percent activity impairment due to AD: $Q6 / 10 \times 100$

These impairment percentages will be summarized by visit and by treatment. Missing values will not be imputed.

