7.4.2. Secondary Efficacy Analysis

All secondary efficacy analyses will be conducted based on the ITT population in the VC and LTS periods.

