7.4.2.1. Continuous Efficacy Endpoints

By-visit summary statistics for the following continuous measurements, including change from baseline and percentage change from baseline will be presented:

- EASI score
- By-visit Itch NRS score
- By-visit Skin Pain NRS score
- By-visit PROMIS Short Form – Sleep-Related Impairment (8a) 24-hour recall total raw score
- By-visit PROMIS Short Form – Sleep Disturbance (8b) 24-hour recall total raw score

The summary statistics includes sample size, mean, median, standard deviation, minimum, maximum, 1st quartile, 3rd quartile, and 95% CI will be presented by visits. An MMRM may be fit for the comparisons between ruxolitinib cream groups and vehicle cream group at Week 8. The MMRM will include the fixed effect of treatment, stratification factor, the visit, and

treatment by visit interaction. The variance-covariance matrix of the within-participant errors in MMRM will be modeled as unstructured.

For the following continuous measurements, the change from baseline to Week 8 will be analyzed using an ANCOVA model with treatment and stratification factors and baseline score as covariates if applicable.

- Total AD afflicted %BSA
- Total SCORAD score
- Total POEM score
- Total DLQI/CDLQI score
- DLQI/CDLQI subscores
- EQ VAS score
- WPAI:SHP v2.0 scores

For the above continuous measurements during the LTS period, only summary statistics will be presented.

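### Week 8 change in %BSA, SCORAD, POEM, DLQI/CDLQI, EQ VAS and WPAI is tested by a single-visit ANCOVA with no missed-visit rule, leaving Week 2 and 4 data unused and out of line with SAP 4.1.5

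*SAP*

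**What the plan says.** SAP 7.4.2.1 splits the by-visit continuous endpoints into two groups.

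- **EASI, Itch NRS, Skin Pain NRS and the two PROMIS scores:** "An MMRM may be fit for the comparisons between ruxolitinib cream groups and vehicle cream group at Week 8". Its listed terms are treatment, stratification factor, visit and treatment by visit, with unstructured covariance. No baseline term is listed.
- **%BSA, SCORAD, POEM, DLQI/CDLQI totals and subscores, EQ VAS and WPAI:** "the change from baseline to Week 8 will be analyzed using an ANCOVA model", adjusted for the strata and, where applicable, the baseline score.

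The general rule in SAP 4.1.5 for continuous endpoints is that "any participant who is missing postbaseline values may have missing data handled using MMRM under the missing-at-random assumption". No other method for missing continuous data is named there.

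For the ANCOVA group, the measure-specific sections of SAP 7.4.1 contain no rule for a missed visit. POEM has an item rule only: "If 2 or more questions are left unanswered, the questionnaire is not scored". DLQI and CDLQI have rules of the same kind. EQ-5D-5L values are not imputed, and for WPAI (SAP 7.4.1.9) "These impairment percentages will be summarized by visit and by treatment. Missing values will not be imputed". The sections on SCORAD and %BSA say nothing about missing values.

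All of these measures are taken at Weeks 2 and 4 (Protocol Table 3 and Section 8.2.7; SAP 7.4.1.4). For SCORAD the SAP says "This will be performed during all VC study visits, starting at baseline". On the population, SAP 7.4.2 says "All secondary efficacy analyses will be conducted based on the ITT population in the VC and LTS periods".

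**The concern.** An ANCOVA of one visit needs an outcome at that visit. With no visit-level rule, anyone lacking a Week 8 score is left out, even if seen at Weeks 2 and 4. The estimate then describes completers, although the population is called ITT.

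The completer ANCOVA is valid only if, given treatment, strata and baseline, being missing at Week 8 is unrelated to the Week 8 score. A repeated-measures model also conditions on the Week 2 and 4 scores, which is a weaker requirement. If participants who respond poorly early on leave more often, and more of them leave one arm, the two arms' completers are selected to different degrees and the contrast shifts. At stake are the Week 8 contrasts for the listed secondary quality-of-life, SCORAD and %BSA endpoints.

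**Working it through.** **Inputs from the documents.** About 600 randomised 2:2:1 gives 600 x 2/5 = 240 per active arm and 600 x 1/5 = 120 on vehicle (Protocol 10.1). In the Phase 2 study 46 of 307 participants discontinued over 8 weeks, 46/307 = 15.0%, not given by arm (Protocol 2.2.2.4.1). No dropout rate is assumed for this trial. The plan states no figure for these endpoints. Its only calculated figure is power above 95% on IGA-TS, and that reproduces with 240 vs 120: Fisher exact power is 98.9% for 30% vs 10% and above 99.9% for 45% vs 10%.

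**Inputs assumed.** Effect size, visit correlation, dropout slope and per-arm dropout.

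**Algebra.** In an arm with dropout p, let D be the completers' mean Week 8 score minus the dropouts' mean, given baseline, with higher meaning better. Completers then exceed the whole arm by p x D. With subscripts A for active and V for vehicle:

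bias of contrast = p_A D_A - p_V D_V

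If D is the same in both arms, this is -(p_V - p_A) x D. It is zero when dropout is equal or when D = 0.

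**Simulation.** 2000 trials per row, 240 vs 120. True effect 0.80 SD at every visit, correlation with baseline 0.3. Dropout after Week 2 or Week 4 has a logit hazard in the last observed score. The comparator is the likelihood repeated-measures estimate with treatment by visit, baseline by visit and unstructured covariance. Monte Carlo error is about 0.12/sqrt(2000) = 0.003.

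| Dropout active/vehicle | Slope | Adjacent-visit correlation | ANCOVA bias (SD) | % of 0.80 | MMRM bias (SD) |
|---|---|---|---|---|---|
| 15%/15% | 0 | 0.6 | 0.00 | 0 | 0.00 |
| 10%/25% | 0 | 0.6 | 0.00 | 0 | 0.00 |
| 15%/15% | 1 | 0.6 | 0.00 | 0 | 0.00 |
| 13%/20% | 1 | 0.6 | -0.030 | 4 | 0.00 |
| 10%/25% | 0.5 | 0.6 | -0.039 | 5 | 0.00 |
| 10%/25% | 1 | 0.6 | -0.063 | 8 | 0.00 |
| 10%/25% | 1 | 0.75 | -0.083 | 10 | 0.00 |
| 10%/35% | 1 | 0.6 | -0.107 | 13 | 0.00 |

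**Cross-check.** Solving the formula for D in the slope 1, correlation 0.6 rows gives 0.030/0.07 = 0.43, 0.063/0.15 = 0.42 and 0.107/0.25 = 0.43, so it describes the simulation well. For 12%/22%, D = 0.42 gives -0.10 x 0.42 = -0.042 SD, or 5% of 0.80.

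**Sensitivity to the assumptions.** With a true effect of 0.90 SD and dropout driven by the Week 4 score alone (correlation 0.6, slope 1), ANCOVA gives 0.88 at 12%/22% (0.02/0.90 = 2% too small) and 0.87 at 10%/25% (3%). Other correlation and slope settings give 0.85 (6%) and 0.83 (8%) for the same two splits. Across all settings the MMRM standard error is up to about 5% lower, and in some it is hardly lower at all.

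**Outside missing at random.** If dropout depends on the unseen Week 8 score (10%/25%, true effect 0.90), ANCOVA gives 0.82 and the likelihood estimate 0.83. Both are biased by nearly the same amount.

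**The case against.** The strongest reply is that both models are standard and prespecified, and that the harm is hypothetical.

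- **No mandatory rule is broken.** A reader might infer that the SAP breaches its own missing-data rule. It does not: SAP 4.1.5, SAP 7.4.2.1 and Protocol 10.4.2 all use *may* for the mixed model. What stands is an unreconciled inconsistency, since the ANCOVA is fixed with *will* and nothing covers a missed visit.
- **Efficacy-driven dropout on vehicle is not shown.** A reader might infer it, but lack of efficacy was the reason for 1 of the 46 Phase 2 discontinuations. Withdrawal by subject (20) and loss to follow-up (13) made up 33. Poor response may lie behind some withdrawals, but the documents do not say so. Completing Week 8 also gives vehicle participants access to active cream, a reason to stay.
- **Some early leavers may have a late value.** Protocol 7.1.2 and 8.7 ask for an EOT visit, and Table 3 puts Week 8 and EOT in one column. The SAP does not say whether an early EOT value counts as Week 8, so this adds to the ambiguity and does not remove it.
- **MMRM's advantage is partly built into the simulation,** because dropout there follows observed scores. That is fair, and the run on the unseen Week 8 score shows the limit of the remedy.
- **The effect is small.** In every row the bias is below one standard error (about 0.12) and, in the direction assumed, towards the null. That also stands.

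**Conclusion.** The point holds as a low-severity matter of analysis choice and clarity. The Week 8 ANCOVA discards observed Week 2 and 4 data for anyone missing Week 8, needs a stricter missingness assumption than MMRM, and is not squared with SAP 4.1.5. That the analysis is confined to completers is an inference from a single-visit model with no visit-level rule. The SAP does not say so in words.

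Under assumed active/vehicle dropout of 12%/22% to 10%/25% driven by earlier response, the contrast is roughly 2% to 8% too small, and 10% at the higher correlation tried. Equal or response-unrelated dropout gives no bias. Heavier dropout on the active arms would reverse the sign of the formula above, so a conservative direction cannot be taken for granted.

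It would be wrong to infer that the trial's main conclusions are at risk. SAP 3.2 limits Type I error control to the primary and key secondary endpoints, and none of these scores is among them.

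**What to change.** In SAP 7.4.2.1, state that these scores *will* be analysed by an MMRM over Weeks 2, 4 and 8 with treatment, visit, treatment by visit, stratification factors, baseline score and baseline by visit, and unstructured covariance. Report the Week 8 contrast and keep the ANCOVA as supportive. Align SAP 4.1.5 with this, and say how an early EOT value is assigned to a visit.

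The MMRM already described for EASI cannot be reused unchanged. It has no baseline terms, so moving these scores to it as written would lose the adjustment the ANCOVA has.

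The SAP should also note that WPAI work scores are structurally missing for participants who are not employed or have no work hours to report. No model recovers those.

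The cost is SAP wording and a little programming, with no new data collection. The downside is reliance on missing at random, which the completer ANCOVA needs in a stricter form.

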7.4.2.2. Daily Continuous Efficacy Endpoints

For the following daily continuous measurements, summary statistics including sample size, mean, median, standard deviation, minimum, maximum, 1st quartile, 3rd quartile, and 95% CI will be presented by day. An ANOVA model will be fit for the comparisons between ruxolitinib cream and vehicle cream at Week 8 on change and percentage from baseline. The ANOVA model will include treatment groups.

- Daily Itch NRS score
- Daily Skin Pain NRS score
- Daily PROMIS Short Form – Sleep-Related Impairment (8a) 24-hour recall total raw score
- Daily PROMIS Short Form – Sleep Disturbance (8b) 24-hour recall total raw score

7.4.2.3. Categorical Efficacy Endpoints

For the following categorical parameters, summary statistics including sample size, frequency, and percentages will be presented by visits.

- Proportion of participants achieving an IGA of 0 or 1
- Proportion of participants with a \geq 2-point improvement in Itch NRS score
- Proportion of participants with a \geq 3-point improvement in Itch NRS score
- Proportion of participants with a \geq 4-point improvement in Itch NRS score
- Proportion of participants achieving EASI50
- Proportion of participants achieving EASI75

- Proportion of participants achieving EASI90
- Proportion of participants with a \geq 6-point improvement in the PROMIS Short Form (8a) – Sleep-Related Impairment 24-hour recall score
- Proportion of participants with a \geq 6-point improvement in the PROMIS Short Form (8b) – Sleep Disturbance 24-hour recall score
- Proportion of participants with a score of either 1 or 2 of PGIC
- Proportion of participants with a clinically meaningful improvement (\geq 4-point improvement) in DLQI/CDLQI

A logistic regression model with treatment and stratification factors as covariates will be fit at Week 8. The p-values between each ruxolitinib group versus vehicle will be calculated based on Wald test. Exact logistic regression will be used for all of the comparisons if any of the dose levels have an expected cell count less than 5. The NRI will be used to impute postbaseline missing values for binary outcomes based on IGA, EASI, Itch NRS, PROMIS Short Form – Sleep-Related Impairment (8a) scores, PROMIS Short Form – Sleep Disturbance (8b) scores.

For the following categorical endpoints, the number and percentage of participants will be summarized by treatment at each postbaseline visit.

- Proportion of participants in each category of EASI score
- Proportion of participants in each category of IGA score
- Proportion of participants in each category of PGIC score
- Proportion of participants in each category of POEM score
- Proportion of participants in each category of DLQI/CDLQI score
- Proportion of participants in each category of each EQ-5D dimension

7.4.2.4. Time-To-Event Efficacy Endpoints

For the time to achieve Itch NRS score improvement of at least 2, 3, or 4 points, a log-rank test stratified by randomization stratification factors will be used for between treatment group comparisons. The hazard ratio and its 95% CI will be estimated based on the stratified Cox regression model using Efron's method accounting for ties. Kaplan-Meier curves will be presented by treatment groups. The number of participants, number of events and number of censoring will be summarized by treatment groups. The KM estimate of median time will be presented with its 95% CI. The 95% CI will be calculated using the method by Brookmeyer and Crowley (1982).

7.6. Pharmacokinetic Analyses

Trough plasma concentrations of ruxolitinib at all study visits will be summarized using descriptive statistics by treatment group.

8. SAFETY AND TOLERABILITY

[Appendix A](#) provides a list of planned tables figures, and listings. Sample data displays are included in a separate document.

8.1. General Considerations

The analyses in this section will be provided for the safety population in the VC and LTS periods. Summary tables may be replaced with listings when appropriate. For instance, an AE frequency table may be replaced with a listing if it only contains a few unique PTs reported on relatively few participants.

Unless otherwise stated, table summaries will be limited to AEs occurring within 30 days of the last application of study drug or the first application in the LTS period (if available) of the study, whichever is earlier.

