Adolescents aged \geq 12 to 17 years, inclusive, and men and women aged \geq 18 years who meet the inclusion criteria and have been diagnosed with AD of at least 2 years duration, an IGA score of 2 to 3, and %BSA involvement of 3% to 20% (excluding scalp) will be enrolled and receive treatment with ruxolitinib 0.75% cream BID, ruxolitinib 1.5% cream BID, or vehicle cream in a 2:2:1 randomization for a total duration of 8 weeks (with a screening period of approximately 28 days) during the VC period of the study. Adolescents will make up approximately 20% of the overall study population.

At Week 8, all participants who successfully complete the VC period of the study and all Week 8 assessments will be offered participation in the LTS treatment period with ruxolitinib 0.75% or 1.5% cream BID. The required %BSA range and IGA score entry into the LTS period is 0% to 20% and 0 to 4 grade, respectively. Participants who were initially treated with either ruxolitinib 0.75% or 1.5% cream will remain in their respective treatment regimen, while those participants who were initially treated with vehicle will be randomized to either ruxolitinib 0.75% or 1.5% cream BID. During this LTS period, participants will have study visits every 4 weeks until the end of the study (52 weeks total).

After the Week 8 visit, during the LTS period, participants will self-evaluate recurrence of AD and will treat those areas of the skin with active AD changes (not to exceed up to 20% BSA). If lesions clear between study visits, participants will stop treatment application 3 days after they have disappeared. In the event that the new lesions are significantly more extensive than from the previous visit, the participant should call the study site to discuss with the investigator whether additional evaluation at the clinic is required. The investigator, if needed, will have the option of having the participant return for an unscheduled visit.

The study schema is shown below in [Figure 1](#). All participants will have follow-up assessments 30 (+ 7) days after the last application of study drug.

Figure 1: Study Design Schema

[figure not shown]

Table 3: Schedule of Activities: Vehicle-Controlled Period

Visit Day (Range)	Screening	Vehicle-Controlled Treatment				Notes
	Days -28 to -1	Day 1 (Baseline)	Week 2 (± 3 d)	Week 4 (± 3 d)	Week 8*/EOT (± 3 d)	
Administrative procedures						
Informed consent (including assent)	X					
Contact IRT	X	X	X	X	X	

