2.3.1. Scientific Rationale for Study Design

This is a confirmatory study in a larger participant population with AD with the objective to further evaluate and confirm the prior findings with regard to the efficacy and safety of the proposed treatment regimens. The population to be studied comprises participants amenable to topical therapy of their AD, \geq 12 years of age with AD lesions covering between 3% to 20% of the total BSA, and IGA of 2 to 3.

Ruxolitinib 1.5% cream BID up to 20% BSA has been well-tolerated in participants with psoriasis, AA, AD and vitiligo clinical studies with few AEs reported and no evidence of systemic effects.

In the dose-range finding study in AD, 1.5% ruxolitinib cream BID for 8 weeks was found to be the most efficacious among investigated study arms with acceptable safety and tolerability profile (see Section [2.2.2.4.1](#) for more details). The maximum clinical effect with this treatment regimen was achieved by Week 8 and did not change significantly thereafter.

[REDACTED]

[REDACTED]

[REDACTED]

[REDACTED]

The randomized LTS period of the study will provide additional safety information when drug is used intermittently for a longer period (up to 44 weeks in total). It will also provide data about the duration of treatment effect after stopping therapy and the nature and number of disease exacerbation (flare) episodes.

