Participants who complete Week 8 assessments with no additional safety concerns will be offered to continue into the LTS period with the same treatment regimen, except for those initially on vehicle, who will be equally assigned at Week 8 to 1 of the 2 active treatment groups. At that time, the IGA score required for the participants to enter the LTS period is 0 to 4. With regard to %BSA, there is no required lower limit; participants may have BSA in the range of 0% to 20%.

In the LTS period, participants will have study visits every 4 weeks until the end of the study (52 weeks total). At those visits, AD lesions will be evaluated by the investigator to confirm if the participant still requires continuation of therapy (IGA ≥ 1) or can otherwise (re)enter the observation/no treatment cycle (IGA = 0).

During the LTS period (ie, after the Week 8 visit), participants will self-evaluate recurrence of AD and will treat areas of the skin with active AD changes (not to exceed 20% BSA). If lesions clear between study visits, participants will stop treatment applications 3 days after they have disappeared. Participants will restart treatment of their AD at the first sign of recurrence. In the event that new lesions are outside of the usual location and/or are more wide spread than at baseline, the participant is required to contact the site for approval. Approval to treat additional areas may occur via telephone during the LTS period, although the investigator, at his/her discretion, may ask the participant to return for an unscheduled visit. This is a close reflection of the clinical practice of managing AD in the outpatient setting.

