During the LTS period starting at the Week 8 visit, participants will have study visits every 4 weeks until the end of the study (52 weeks total). At those visits, AD lesions will be evaluated by the investigator to confirm whether the participant still requires continuation of therapy (IGA ≥ 1) or can otherwise (re)enter the observation/no treatment cycle (IGA = 0). At Week 8, a participant will receive a prespecified number of tubes with study medication corresponding to a lower %BSA affected (up to 5%) or higher number of tubes corresponding to their affected %BSA ($> 5\%$). This new estimate will be entered into the IRT system to calculate the number of tubes of study drug to be dispensed.

In-between study visits, the participant will self-evaluate recurrence of AD and will treat all areas identified with active AD changes (not to exceed 20% BSA). If lesions clear between study visits, participants will stop treatment applications 3 days after they have disappeared. Participants will restart treatment of their AD at the first sign of recurrence. In the event that new lesions are outside of the usual location and/or are more widespread than at baseline, the participant is required to contact the site for approval. Approval to treat additional areas may

occur via telephone during the LTS period, although the investigator, at his/her discretion, may ask the participant to return for an unscheduled visit.

Application instructions will be provided by the site study staff, and the participant will record their daily applications via a diary card given to the participants during each study visit. Refer to the Study Pharmacy Manual for participant instructions for handling study of drug. [Table 6](#) presents the study treatment information.

Table 6: Study Treatment Information

	Study Treatment 1	Study Treatment 2	Study Treatment 3
Study treatment name:	Ruxolitinib	Ruxolitinib	Vehicle
Dosage formulation:	Cream	Cream	Cream
Unit dose strength(s)/dosage level(s):	0.75%	1.5%	Not applicable

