8.8. Safety Follow-Up

The safety follow-up period is the interval between the EOT visit and the scheduled follow-up visit, which should occur 30 (+ 7) days after the EOT visit (or after the last dose of study drug/treatment if the EOT visit was not performed).

Adverse events and SAEs must be reported up until at least 30 days after the last dose of study drug/treatment, the date of the follow-up visit, or until toxicities resolve, return to baseline, or are deemed irreversible, whichever is longer. Reasonable efforts should be made to have the participant return for the follow-up visit and report any AEs that may occur during this period.

9. ADVERSE EVENTS: DEFINITIONS AND PROCEDURES FOR RECORDING, EVALUATING, FOLLOW-UP, AND REPORTING

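### The single 30-day cut in SAP 8.1 makes it depend on later recurrence whether a long-term adverse event is tabulated

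*SAP*

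**What the plan says.** **Tabulation rule.** SAP 8.1 sets a default from which the SAP may depart by saying so: "table summaries will be limited to AEs occurring within 30 days of the last application of study drug". A second limb brings the limit forward for anyone who enters the LTS: "or the first application in the LTS period (if available) of the study, whichever is earlier". No separate LTS window appears elsewhere in SAP Section 8 or in the Appendix A table titles. Appendix A does plan AE tables for the LTS period and for Baseline to Week 52.

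**TEAE definition.** SAP 8.2.1 counts any AE that is new or worse after first administration. It sets no end date and does not exclude time off drug. The AE summaries in SAP 8.2.2 are numbers and percentages of participants; none is adjusted for exposure. Listings keep every AE whatever its timing.

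**LTS use.** Protocol 2.3.1 describes the LTS as giving safety information "when drug is used intermittently for a longer period (up to 44 weeks in total"). At each visit a clear participant "can otherwise (re)enter the observation/no treatment cycle (IGA = 0"), according to Protocol 4.1. Protocol 6.1 adds: "If lesions clear between study visits, participants will stop treatment applications 3 days after they have disappeared". Treatment restarts at the first sign of recurrence. Visits continue every 4 weeks to Week 52, and Protocol Table 4 has AE assessment at each.

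**Follow-up anchor.** Protocol Section 1 says: "All participants will have follow-up assessments 30 (+ 7) days after the last application of study drug". Table 2 in that same section allows either the last application or the last visit. Protocol 8.8 describes a follow-up visit "which should occur 30 (+ 7) days after the EOT visit", or after the last dose if there was no EOT visit. SAP Section 3 uses the last application.

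**The concern.** A window hung on one last application suits continuous dosing. Here drug-free gaps are part of the design, and the SAP expects them: Appendix A plans a Kaplan-Meier curve of time to first retreatment.

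With this anchor, two participants can have the same event at the same time in the same drug-free gap and be treated differently. If one of them later applies cream, the event is tabulated; if the other never does, an event more than 30 days into the gap is not. Inclusion of an event then depends on something that happens after it, namely recurrence of the disease.

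Long-term safety is the purpose of the LTS, and the sample size was set partly to give an adequate safety database (Protocol 10.1). A participant whose window closes early stays in the denominator of every percentage while later events leave the numerator. This applies equally to the serious, fatal and Grade 3 or higher tables.

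**Working it through.** The plan states no figure to reproduce. The check is calendar arithmetic.

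**Inputs.** Window of 30 days after the last application (SAP 8.1); LTS from Week 8 to Week 52, which is 44 weeks (Protocol 4.2); visits every 4 weeks whether or not cream is in use (Protocol 4.1).

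**Step 1: which limb governs the LTS.** Taken literally, the earlier of the two limits would stop tabulation for every LTS entrant at the first LTS application. That would empty the planned LTS tables and reduce the Baseline-to-Week-52 tables to the vehicle-controlled period. That limb can only be meant for the vehicle-controlled tables, which leaves the 30-day limb for the LTS.

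**Step 2: time lost before Week 52.** Window end = week of last application + 30/7, that is + 4.3 weeks. Weeks lost = 52 − window end, or 0 if negative. Share = weeks lost / 44.

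| Last application | Window ends (week) | Weeks lost before Week 52 | Share of LTS |
|---|---|---|---|
| Week 12 | 16.3 | 35.7 | 81% |
| Week 24 | 28.3 | 23.7 | 54% |
| Week 32 | 36.3 | 15.7 | 36% |
| Week 40 | 44.3 | 7.7 | 18% |
| Week 51 | 55.3 | 0 | 0% |

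The asymmetry is in the Week 24 and Week 51 rows. Take two participants who both stop at Week 24. If the first makes no further application, 23.7 weeks go untabulated. If the second applies once at Week 51, the whole gap is tabulated.

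**Step 3: counting through follow-up.** Let follow-up end 30 days after Week 52: day 364 + 30 = 394. The LTS starts on day 56, so the span is 394 − 56 = 338 days. Days lost = 394 − (day of last application + 30).

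- Week 12 (day 84): 394 − 114 = 280 days, 83%.
- Week 24 (day 168): 394 − 198 = 196 days, 58%.
- Week 36 (day 252): 394 − 282 = 112 days, 33%.
- Week 48 (day 336): 394 − 366 = 28 days, 8%.

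**Step 4: what this could mean for event counts.** This needs two assumptions that are not in the documents: a constant AE rate, and a share f of participants who make no further application. Share of LTS events untabulated = f × share of days lost.

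- f = 10%: from 0.10 × 28/338 = 0.8% (last use Week 48) to 0.10 × 280/338 = 8.3% (Week 12).
- f = 30%: from 0.30 × 28/338 = 2.5% to 0.30 × 280/338 = 24.9%.

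These are shares of events. The effect on a percentage of participants may be smaller, because someone already counted for a term before the cut stays counted.

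**The case against.** **Protocol Table 4 may close most of the gap.** It marks study drug application at every LTS visit from Week 12 to Week 52 with no IGA condition, and Protocol 6.1 has the first application on visit days done at the clinic. If clear participants also applied cream at each visit, the window would seldom close early. But this conflicts with the no-treatment cycle in Protocol 4.1 and 6.1, and with Protocol 6.5, which confines LTS treatment to areas with active disease. The documents do not settle which governs. The arithmetic above holds only where no application is made during a no-treatment cycle.

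**A 30-day window is conventional.** It matches the protocol's minimum AE monitoring period (Protocol 8.3.1) and the SAP's last-available-value rule (4.1.4), and it avoids counting events remote from exposure. That is a good reason to keep it as an on-treatment analysis. It does not explain why an equally remote event is counted when an application happens to follow.

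**No data are lost.** This stands. Protocol 8.8 collects AEs to the longest of several limits, Protocol 9.4 collects SAEs to the later of two, and the listings keep everything. The issue is confined to the summary tables, but reported incidences come from those.

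**Long final gaps may be rare.** Protocol 2.3 describes the disease as chronic and relapsing. That is fair, and the documents give no figure either way.

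**A stronger reading is tempting:** that the rule flatters the 1.5% cream, since Protocol 10.1 assumes higher Week 8 success at 1.5% than at 0.75% (45% against 30%). That assumption concerns response at one visit. It does not show how many in either arm stay off cream for more than 30 days up to the end of the study. A biased dose comparison is possible but not shown.

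**Conclusion.** The point holds as a defect in the tabulation rule. On the only workable reading of SAP 8.1 for the LTS, the final drug-free gap is cut at 30 days while any earlier gap is counted in full, so inclusion of an event depends on later recurrence. Compared with counting all on-study events, an affected incidence can only be understated.

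For an individual the loss before Week 52 is large if the last application is early (23.7 weeks for Week 24) and nil if it is late. For the trial the size is unknown, because the share ending in a drug-free cycle is not given, nor its split by dose. The 54% for Week 24 is one hypothetical participant's share of LTS time. A reader might take it as a share of events missing from the tables, and it is not that.

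The conclusion rests on two assumptions: that the limb about the first LTS application belongs to the vehicle-controlled tables, and that clear participants make no clinic application at LTS visits.

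The differing follow-up anchors are a separate inconsistency. They cost no AE data under Protocol 8.8, but for a participant in a drug-free cycle they can point to dates weeks or months apart.

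**What to change.** 1. In SAP 8.1, give each period its own AE window. Assign the limb about the first LTS application to the vehicle-controlled tables. For the LTS and Baseline-to-Week-52 tables, end the window at the later of the EOT (or last LTS) visit and 30 days after the last application.
2. Keep the 30-day cut for those tables as a supplementary on-treatment analysis.
3. Reconcile the application row in Protocol Table 4 with the no-treatment cycle in Protocol 4.1, 6.1 and 6.5.
4. Reconcile the follow-up anchor across Protocol Section 1 (both wordings), Protocol 8.8 and SAP Section 3.

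With step 1, the Week 24 participant is tabulated to Week 52 and none of the 23.7 weeks is lost. Time between EOT and the follow-up visit stays outside the main table for someone already more than 30 days off cream at EOT; ending at the follow-up visit would include it too.

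The cost is SAP wording, one date derivation and a supplementary set of tables, all from data already collected. The drawback is that the main tables will hold some events remote from exposure, and the supplementary table lets a reader judge those.
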